## RESEARCH DESIGN AND METHODS

Previous Research: With funding from the Greater Wisconsin Agency on Aging Resources, research was conducted to develop an intervention to reduce sedentary behavior and examine the feasibility of implementing the intervention by a State Aging Unit in a community setting. The research was conducted in two communities in Rock County, Wisconsin which is made up of

small urban and rural communities. The older adults in these communities had high levels of sedentary behavior (averaging almost 11 hours of their waking hours per day sitting) and their function scores were below the population average. A 4-week intervention based on self-regulation theory and designed to break up extended sitting time by standing up multiple times during the day significantly ( $p < 0.05$ ) reduced sedentary behavior (60 min/day), was associated with moderate increases in light intensity physical activity (effect size = 0.52; 35 minutes/day), and large effect size improvements in mobility (i.e., gait speed; effect size = 0.74) as well as vitality (effect size = 1.15). Importantly, reductions in sedentary behavior were sustained 4 weeks after the intervention ended. Strategies used most often included standing up during television commercials, and spreading household chores out across the day. Additional strategies included getting up to get a drink of water, and setting a timer to stand up. Twenty participants (out of a total of 25) completed the 4-week program and 90% of the participants expressed high satisfaction with the program (e.g., “What a great program. It made me realize how much I sit during the day and helped me manage my sitting time”). Also, participants indicated that breaking up sitting time was more appealing to them than increasing exercise. Further, the intervention was found to be feasible for staff to implement. The director of the Rock County Council on Aging who led the workshops stated “The intervention worked because it was simple. It is not complex and that is the beauty of it.” Thus, our pilot results are quite promising and represent the development, preliminary feasibility, and piloting stages of the *Stand Up & Move More* intervention in a small sample of older adults.

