**Design:** As a next step, a randomized controlled trial will be conducted with a larger sample of older adults from underserved communities. Older adults from 4 counties in Wisconsin (i.e., Dane, Iowa, Rock & Vilas) will be randomized into intervention or wait-list control groups (Note: a block randomization scheme will be used blocking for age). Our pilot data suggests an intervention design of one session per week for 4 weeks with a refresher session at 8 weeks is feasible and likely to sustain behavior change. The primary outcome measure is sedentary behavior while the secondary outcome measures include physical activity, functional performance, and health-related quality of life. Assessments will be completed at baseline, after the intervention (4 weeks) and at follow-up (at 12 weeks as suggested by our community partners as being a reasonable time for the older adults in the control group to wait for the next workshop to begin). Feasibility of implementing the intervention will be assessed via semi-structured interviews of the health program facilitators, while feasibility of completing the *Stand Up & Move More* program by older adults will be assessed by program adherence and participant satisfaction.

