**Participants:** A power analysis was performed to estimate optimal sample size for detecting potential differences between intervention and wait-list control groups in sedentary behavior using a repeated measures design, with an alpha of 0.05, a power of 0.80, and a medium effect (0.57). Results from the G-power analysis indicated a total of 68 participants (34 per group) would be needed for the proposed study but we have increased sample size in anticipation of a potential attrition rate of approximately 20% (a minimum of 80 adults older than 55 yrs will be recruited). Four counties (Rock, Iowa, Vilas & Dane) will each recruit between 20–30 older adults who will be randomized to either the intervention group ( $n = 10–15$ ) or the control group ( $n = 10–15$ ). Inclusion criteria includes > 55 yrs, currently inactive or low active (i.e., < 60 min of physical activity/week), residents of Rock, Iowa, Vilas or Dane Counties, and residing in a home or an apartment. Exclusion criteria are low levels of sedentary behavior (i.e.,  $\leq 6$  hours/day); recent hospitalization (past month); uncontrolled medical conditions including uncontrolled hypertension (BP > 170 systolic or 100 diastolic), heart disease (symptoms of angina with minimal exertion in the past month), actively receiving chemotherapy or palliative care for cancer, stage 4 liver disease (e.g., cirrhosis with ascites or encephalopathy or history of

bleeding esophageal varices), end-stage renal disease (on dialysis or creatine > 4), or end-stage pulmonary disease (dyspnea at rest or with minimal exertion); severe arthritis or any orthopedic condition that could be made worse by standing up and moving more; inability to stand up without assistance of another person; and inability to speak or hear spoken English. Participants will be given a gift card up to \$50 upon study completion (\$20 for participating in the study plus \$10 per each of three assessments).

Recruitment of Participants: Staff from Aging Units in the four counties will recruit older adults from their counties for this study. Recruitment strategies include announcements in senior newsletters, at congregate dining sites, churches, and medical clinics. In addition, announcements will be posted on Aging Unit websites, and flyers will be sent to mailing lists of older adults in the various counties. These strategies were used in our pilot research and worked well in recruiting the estimated sample size.

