*Demographic and Health History Questionnaire*: At baseline, participants will be asked to complete a questionnaire regarding health status and demographic information (date of birth, sex, race, ethnicity, education, and marital status), current physical activity, smoking status, and current alcohol intake.

*Mediators of Behavior Change*: As suggested by NIH reviewers, we have added selected mediators of behavior change. Participants will complete questionnaires assessing self-regulation strategies, self-efficacy, and outcome expectancies.

*Adherence to the Intervention and Outcome Assessments*: Adherence to the *Stand Up and Move More* intervention workshop will consist of participants attending at least 50% of the sessions. As for outcome assessments, adherence to wearing the accelerometers will be defined as wearing the monitors 4 out of 7 days.

*Analyses*: The primary sedentary behavior outcome variables include total sedentary time, time spent sitting in long bouts (i.e.,  $\geq 60$  minutes), and sit-to-stand transitions as measured by the activPAL. These outcomes will be examined adjusting for monitor wear time if wear time differs between groups. We will also be able to analyze changes in specific domains of sedentary behavior (e.g., watching TV, reading) from data obtained from the sedentary behavior questionnaire. A 2 (groups) x 3 trials (pre, post-1, and post-2) repeated measures ANOVA will be used to examine differences between groups in changes in sedentary behavior before and following the intervention and control conditions. Similarly, for the secondary variables of physical activity, functional performance, health-related quality of life, and mediators of behavior change, a series of 2 x 3 repeated measures ANOVA's will be performed. Significant main effects and interactions will be assessed with planned contrasts. Effect sizes will be calculated to examine the magnitude of differences between groups as well as the magnitude of change from pre to post-intervention according to methods described by Cohen. In addition,

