correlational analyses will be performed to examine the relationship between sedentary behavior and the secondary outcomes. Significance will be set at  $p < 0.05$ . {Note: since sample size was estimated for our primary outcome variable of sedentary behavior, we recognize the potential limitation of our sample for secondary outcomes. However, if one or more of the secondary outcomes shows a trend in the direction of significance and/or shows a moderate to large effect size, the number of participants can be expanded in subsequent research to address a specific hypothesis}.

*Note:* Multiple imputation will be used to account for missing data (and attrition) under a missing-at-random assumption using MICE package in R. Longitudinal models for the outcomes at the two post-intervention visits will adjust the pre-intervention value as a covariate and explicitly model changes in the outcomes over time. Intervention workshop will be included in the included model as a random effect to account for correlations in outcomes between subjects in the same workshop.

Feasibility: The feasibility of implementing the program by our community partners will be assessed after the refresher session (at 8 wks) via semi-structured interviews. The Aging Unit Directors and Health Program Facilitators will be interviewed and asked about their satisfaction with the intervention, the ease and difficulty of implementing the program, and their likelihood of sustaining the intervention outside of a research study {*Note: Aging Units offer evidence-based health promotion programs to older adults in their counties which are funded by the Older Americans Act (OAA). When a new health promotion program is shown to be evidence-based (i.e., effective, translatable), Aging Units can use OAA funding to support and sustain implementation of the program*}. Interviews will be transcribed and coded, classified, and organized into main themes using thematic analyses. Feasibility of completing the program by older adults will be assessed after the refresher session (at 8 wks) on the basis of program adherence (i.e., attendance) and participant satisfaction (brief questionnaire).

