**Table 2. Schedule of Assessments**

Assessments	Introductory Meeting	Session 1	Session 2	Session 3	Session 4	Refresher Session 8 wks	Follow-up 12 wks
Informed Consent	X						
Demographic/health questionnaire	X						
SF-36	X				X		X
PROMIS questionnaires	X				X		X
Sedentary Behavior interview	X				X		X
Self-efficacy questionnaire	X				X		X
Self-regulation questionnaire	X				X		X
Outcome expectations questionnaire	X				X		X
Short Physical Performance Battery	X				X		X
Accelerometers	X				X		X
Adverse events			X	X	X	X	X
Fidelity monitoring		X	X	X	X	X	
Satisfaction						X	
Feasibility						X	
Cost estimate							X

Note. Screening of prospective participants and randomization will be completed prior to the introductory meeting.

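### Participant satisfaction is scheduled once, at the week-8 refresher, with no stated way to reach those who miss it, so the result is likely to reflect retained participants

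*Combined protocol and SAP*

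**What the plan says.** The Design paragraph of the protocol states that feasibility for older adults "will be assessed by program adherence and participant satisfaction". The Feasibility paragraph repeats the two components, "on the basis of program adherence (i.e., attendance) and participant satisfaction (brief questionnaire"), and gives the time: "Feasibility of completing the program by older adults will be assessed after the refresher session (at 8 wks").

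In Table 2 (Schedule of Assessments), the row "Satisfaction" has one mark, in the column "Refresher Session 8 wks". There is none at Session 4 or at the 12-week follow-up.

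Adherence to the "intervention workshop will consist of participants attending at least 50% of the sessions". On loss of participants, the sample size paragraph adds people "in anticipation of a potential attrition rate of approximately 20" per cent. The Previous Research paragraph reports for the pilot: "Twenty participants (out of a total of 25) completed the 4-week program and 90% of the participants expressed high satisfaction with the program".

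The documents do not say who receives the satisfaction form, how anyone absent from the refresher would get it, what the denominator is, or how missing responses are handled. Multiple imputation is described next to the longitudinal outcome models and is not said to cover satisfaction.

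**The concern.** A satisfaction survey tied to a late session tends to hear from people who are still attending. Those who left, or who missed week 8, may think differently of the programme, and their views are the ones an Aging Unit would want when deciding whether to keep offering it. Attendance shows that a person stopped. It does not show why, or what they thought.

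The gap is also wider than dropout. A person can meet the adherence criterion, even attend every weekly session, and still be absent at week 8.

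At stake is the meaning of one of the two participant measures under Aim 2. The primary outcome and the staff interviews are untouched. Unlike a reporting choice, this cannot be repaired afterwards, because the missing answers would never have been collected.

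**Working it through.** The plan states no satisfaction target or expected response rate, so there is no planned figure to reproduce. The check has three steps.

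**1. Is there a documented route to non-attenders?**
- Table 2: one satisfaction mark, at the week-8 refresher.
- Data Collection section: research assistants travel to the sites at baseline, after the 4-week intervention and at 12 weeks. No week-8 trip is listed.
- The only week-8 contact with participants that is described is the refresher itself.

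So, as written, a person absent at week 8 has no stated way to receive the form. This includes adherent people: attending all four weekly sessions gives 4/4 = 100% of sessions if the refresher is not counted and 4/5 = 80% if it is. Both exceed the 50% criterion.

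**2. The pilot figure.** 20 of 25 completed, and 90% reported high satisfaction, with the denominator not stated.
- Out of 20: 18/20 = 90% exactly.
- Out of 25: 22/25 = 88% and 23/25 = 92%, so no whole number gives 90%.

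The 90% therefore most likely counts completers only, although the text does not say so. If it does, satisfaction over all 25 lies between 18/25 = 72% (none of the five others satisfied) and (18 + 5)/25 = 92% (all five satisfied).

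**3. Bounds for this trial (illustration).** Inputs: 40 allocated to the intervention (Précis); satisfied share among those surveyed p = 0.90 (assumed, borrowed from the pilot); share not surveyed u (assumed, varied).

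Lower bound = p(1 − u). Upper bound = p(1 − u) + u. If half of those not surveyed were satisfied (a further assumption), the surveyed figure exceeds the all-allocated figure by 0.90 − [0.90(1 − u) + 0.50u] = 0.40u.

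| u | Surveyed of 40 | Lower | Upper | Excess if half of the rest are satisfied |
|---|---|---|---|---|
| 10% | 36 | 32.4/40 = 81% | 36.4/40 = 91% | 4 points |
| 20% | 32 | 28.8/40 = 72% | 36.8/40 = 92% | 8 points |
| 30% | 28 | 25.2/40 = 63% | 37.2/40 = 93% | 12 points |
| 40% | 24 | 21.6/40 = 54% | 37.6/40 = 94% | 16 points |

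The width of each interval equals u, so uncertainty grows one for one with the share not surveyed. Every upper bound is slightly above 90%, so the arithmetic alone does not fix the direction of any bias.

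**The case against.** A reader might infer that the form goes only to people in the room at the refresher, that dropouts are therefore left out of feasibility, and that feasibility is overstated. The documents do not support any of these as fact.

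- **Only attenders.** The text gives a time, after the refresher, and not a mode of delivery. Table 2 columns partly mark timing. The feasibility row sits in the same column but refers to interviews with directors and facilitators. The Session 4 column carries the 4-week assessments that wait-list controls also complete, although they attend no workshop then. A manual of procedures, not available here, may settle distribution. This objection stands: restriction to attenders is an inference. What remains is that no other route is stated.
- **Dropouts excluded.** Attendance is the other participant measure, and nothing limits it to those who stay. A person who leaves counts against it. This stands, and it confines the point to satisfaction.
- **Feasibility overstated.** The bounds straddle 90%, no threshold is given, and reasons for absence could be illness or scheduling as well as dissatisfaction. This stands: overstatement of satisfaction is likely, not shown. Nor do the documents weight the two measures, so satisfaction cannot be called half of the evidence. The Aim 2 hypothesis concerns implementation by Aging Units, which rests mainly on the staff interviews.
- **The 20% figure.** It is attrition across the whole trial, used for sample size, and not refresher absence or questionnaire non-response. This also stands, which is why a range is shown.

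None of this supplies a way to hear from people absent at week 8.

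**Conclusion.** The point holds in limited form. Satisfaction has a single scheduled collection, at the week-8 refresher, and the plan states no route to people who miss that session or leave, including adherent participants. The result is therefore likely, but not certain, to reflect retained participants.

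Its size depends on how many are not surveyed and what they think, neither of which the documents give. With 90% assumed among those surveyed, all-allocated satisfaction would be 72% to 92% at 20% not surveyed, with the narrower and wider ranges shown in the table. These are illustrations, not forecasts, and they treat all 40 as able to rate the programme. Because no threshold is stated, no trial decision can be shown to change. It is a worthwhile, inexpensive improvement to a secondary aim.

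**What to change.** In the Feasibility paragraph and in Table 2:

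- Offer the same brief questionnaire to every intervention participant who attended at least one session and has not declined further contact. For those absent from the refresher, use mail or telephone at week 8. Ask non-responders again at the existing week-12 visit.
- Add one item on the reason for stopping or for missing sessions.
- Report the response rate, satisfaction among respondents, and attendance against the 50% criterion over all allocated to the intervention. Give simple lower and upper bounds for satisfaction non-response. State how many never attended; they count in attendance but cannot rate the programme.

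The cost is a few mailed forms or short calls: 8 people if 20% of 40 are absent (0.20 × 40), 12 if 30% are. Some will not reply, and the reported figure may be lower than one from refresher attenders alone. Using the form in the wait-list workshops as well is optional; it would add respondents but would not address this selection.

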## **SAFETY**

### ***Data Safety & Monitoring Plan***

#### **1). Participants Safety:**

##### Potential Risks and Benefits for Participants

*Risks:* Participants will be asked to think of things they can do safely in their home to break up prolonged sitting time (e.g., stand up during TV commercials). The intervention should pose minimal risk of falling or injury since the participants will only be asked to engage in activities that are a part of their normal routine. There may be a risk of muscle soreness or increases in pain upon standing up and moving more. In addition, when completing the functional assessments (i.e., balance and chair stand tests), there may be risks of falling, muscle soreness, and pain. There also may be a risk to confidentiality, however, ID numbers will be used in place of participants' names on documents related to this study.

*Potential Benefits:* Older adults are the most sedentary age group spending 60-70% of their waking hours sitting. This amount of sitting time increases the risk of functional decline, chronic diseases, and premature mortality. The potential benefit of the proposed research to participants is acquiring knowledge on the negative health consequences of sedentary behavior (e.g., increased risk of obesity, metabolic syndrome, type 2 diabetes, cardiovascular disease, some malignancies, and premature death), and developing strategies to reduce sedentary behavior. Sitting less seems simple but intervention is required to get older adults to do it. If breaking up sitting time by standing up and moving more throughout the day proves to be effective, as our pilot data suggests, then we will have identified a practical intervention with the potential to improve the health and function of older adults.

Adverse Event and Serious Adverse Event Collection and Reporting: Adverse events are not expected to occur. The health program facilitators will, however, at the beginning of each workshop session, distribute a brief questionnaire asking about any adverse events (e.g., falling while standing up, injury, muscle soreness, and/or increases in pain) that may have occurred during the previous week. Other information to be gathered at the beginning of each session includes whether any of the participants were sick or sought healthcare during the past week. The health program facilitators will review the responses and then follow-up with respondents during the break or at the end of the session. (Note: the health program facilitators will be trained by [name] to assess adverse events as part of a day-long ‘Stand Up and Move More’ workshop training session for the community partners). Adverse events (AE) occurring during the study will be documented and reported (to the DSMB, IRB, and NIA) by the Principal Investigator (PI). The occurrence of AEs will be assessed on an ongoing basis during the intervention. If patterns of recurrent AEs across participants suggest modifications of the study protocol are required, such changes will be implemented in consultation with NIH staff and the IRB of record. The PI will be responsible for ensuring participant safety on a daily basis. The PI or research assistant will call the health program facilitators on a weekly basis during the workshop to discuss safety concerns and delivery of intervention content. In addition, bi-weekly phone calls will occur with the PI, [name], and [name] (for quality assurance). A Data and Safety Monitoring Board (DSMB) will oversee safety monitoring and will act in an advisory capacity to the NIA Director to monitor participant safety.

Protection Against Study Risks:

*Informed Consent Process:* The consent process will inform volunteers about the study, indicate participation is voluntary, and that she/he has the right to stop at any time. Risks and benefits will be enumerated in the consent form and described orally during the consent process. An introductory meeting will be held for individuals who are interested in participating in this study. An explanation of the study will be given and questions will be answered. Participants will read and sign an IRB-approved consent form. Consent will be obtained by qualified personnel affiliated with the study including the PI and/or research assistants. All participants will receive a copy of their signed consent form.

*Protection Against Study Risks:* Participants will be asked to think of things they can do safely in their home to break up extended sitting time (i.e., 1 hour or more). The first session of the 4-week workshop will contain a discussion of how participants could stand up and move more safely in their homes (with consideration of any existing chronic pain conditions). When they make their action plans they will think about how to do the activity safely (e.g., is the chair safe

to rise out of? Do they need something to hold onto? What will they use?). Participants will also identify things they should not do, and there will be a discussion on care in case of injury (e.g., call 911 as needed, as they would do in any other incident at home, and be seen by their regular clinical care system for diagnosis, treatment and follow-up. Participants will be instructed on what to report and to whom if they have an adverse event while participating in the workshop). Also, during weekly meetings, participants will report on any situation that arose during their efforts to break up their sitting time (e.g., muscle soreness and/or increases in pain), and then problem solve with input from the health program facilitators (e.g., trying alternative strategies, reducing the number of stands until the soreness subsides, etc). The PI or research assistant will call the health program facilitators on a weekly basis to discuss safety issues & delivery of the intervention, and bi-weekly phone calls will occur with the PI, [name], and [name] (for quality and safety assurance). [name] has an extensive background in falls prevention. She founded and serves as medical director of the multidisciplinary UW-Health Geriatric Falls Clinic. [name] has researched and published extensively on falls prevention and mobility in older adults and is providing falls prevention expertise for this study. {Note: in our previous preliminary research, there were no injuries and pain did not increase even though the majority of the participants reported having arthritis}. When completing the physical function assessments (i.e., balance and chair stand tests), there are minimal risks of falling, muscle soreness, and/or increases in pain. However, to reduce these risks the physical function tests will be conducted near a table or wall in case a participant needs to steady themselves (in case they begin to fall). Also, the assessor will be close enough to the participant to catch them if need be.

Risks to confidentiality will be minimized by using ID numbers in place of names on all documents related to this study. The only document linking study assignment number and the subject's unique identifiers (along with signed informed consents) will be kept in a locked cabinet in [name] office. Data will be stored in a password protected area with firewall protection and double backed up on flashdrives on the day of data collection. These back-up copies will be kept in a locked cabinet in the laboratory of [name]. Accuracy of data entry by the research assistant will be checked by [name] on a regular basis.

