## PRÉCIS

Title: Translating a ‘Stand Up and Move More’ Intervention by State Aging Units to Older Adults in Underserved Communities

Objectives: To examine the effectiveness of a *Stand Up and Move More* intervention to reduce sedentary behavior, increase physical activity, and improve functional performance and quality of life in older adults. A second objective is to examine the feasibility of implementing the *Stand Up and Move More* intervention by State Aging Units to underserved communities in the state.

Design and Outcomes: A randomized controlled trial will be conducted with older adults from four counties in Wisconsin (i.e., Dane, Rock, Iowa, and Vilas counties) randomized to intervention or wait-list control groups. Sedentary behavior, physical activity levels, functional performance, and health-related quality of life will be assessed at baseline (before the intervention begins), at week 4 (after the intervention), and week 12 (follow-up) to examine the effectiveness of the program. Feasibility of implementing the program by our community partners will be assessed via semi-structured interviews.

Intervention and Duration: The intervention consists of an introductory session, four weekly sessions (i.e., once/week for four weeks), and a refresher session at 8 weeks, and will be delivered by community partners in each county. Based on self-regulation theory, the sessions will elicit ideas from older adults regarding how they can reduce their sitting time, help them set practical goals, develop action plans to reach their goals, and refine their plans across sessions to promote behavior change.

Sample Size and Population: Eighty sedentary adults greater than 55 years of age from four counties made up predominantly of rural older adults and older African American adults will be randomly assigned to intervention (n = 40) or wait-list control (n = 40) groups.

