Session 4	
Record time spent sitting/day (to compare to week 1)
 
Discuss goals and behaviors from previous week
 
Discuss relapsing back into old patterns & how to stay motivated
 
Review benefits of standing up and moving more
 
Discussion of how to stay active in the community
 
Modeling (group leader stands and encourages others to stand and move)
 
Set a new goal (i.e., long-term goal: what to do after this program ends)
 
Develop an action plan to meet the goal
 
Self-monitoring (discuss self-monitoring during the past week & monitoring plans for long-term success)

Refresher Session	
Re-examine motives for sitting less
 
Discuss progress and barriers
 
Share strategies to stand up & move more that worked well
 
Revisit goal with a focus on how to maintain new behaviors over the long-term
 
Modeling (group leader stands and encourages others to stand and move)
 
Congratulate the participants and discuss ongoing activities & social events

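### Adverse-event enquiry is tied to workshop sessions with a one-week recall, so some weeks are never asked about and no method is given for controls

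*Combined protocol and SAP*

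**What the plan says.** **Collection rule.** Under Adverse Event and Serious Adverse Event Collection and Reporting, facilitators will, "at the beginning of each workshop session, distribute a brief questionnaire asking about any adverse events", covering events "that may have occurred during the previous week". Questions on illness and healthcare use have the same one-week look-back. The section also states that "Adverse events (AE) occurring during the study will be documented and reported" by the principal investigator, and that "The occurrence of AEs will be assessed on an ongoing basis during the intervention". The investigator or a research assistant will "call the health program facilitators on a weekly basis during the workshop"; these calls go to facilitators, not participants.

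**Session timing.** The Précis describes the intervention as "an introductory session, four weekly sessions (i.e., once/week for four weeks), and a refresher session at 8 weeks". Table 1 lists the "Refresher Session" with the group workshop sessions.

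**Schedule.** In Table 2 the row "Adverse events" is marked at Sessions 2, 3 and 4, the week-8 refresher and the week-12 follow-up. It is blank at the introductory meeting and Session 1. The row gives no recall period, method, assessor or arm.

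**Controls.** Under Wait-List Control Group, controls keep to their usual routines for 12 weeks and receive the workshop afterwards. They complete the baseline, week-4 and week-12 assessments as the intervention arm does. The Measures section lists no adverse-event enquiry among those assessments.

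**The concern.** The only described way of asking about adverse events depends on attending a workshop session. Attendance is what differs between the arms by design, and in the intervention arm it stops for several weeks before the refresher. Followed as written, the rule leaves stretches of the study unasked and reaches controls not at all before week 12.

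The plan commits to documenting events that occur during the study, and under DSMB Responsibilities the board advises on continuation in light of observed adverse effects. A pooled count would miss events in unasked weeks. A count by arm could show more events in the intervention arm only because that arm is asked about more weeks.

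**Working it through.** There is no stated figure to reproduce. The check counts which of the 12 weeks (84 days) before controls start their workshop are covered by an enquiry.

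**Inputs from the documents:** sessions once a week for four weeks and a refresher at week 8 (Précis); one-week recall on session forms (Safety section); the adverse-event marks in Table 2; no workshop for controls before week 12 (Wait-List Control Group).

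**Assumptions, because the documents are silent:** the recall at the week-12 visit, and at the week-4 visit if it asks at all, is first set to one week. Full attendance is assumed, and spontaneous reports are not counted. A contact on day *d* covers days *d* − 7 to *d*.

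**Intervention arm, one-week recall throughout**
- Sessions at the ends of weeks 1-4, Session 1 counted (as the Safety section implies): weeks 1, 2, 3, 4, 8 and 12, so 6 × 7 = 42 of 84 days.
- Same timing, Session 1 not counted (as in Table 2): weeks 2, 3, 4, 8 and 12, so 5 × 7 = 35 of 84 days.
- Session 1 on day 0 and Session 4 on day 21: weeks 1, 2, 3, 8 and 12, so 35 of 84 days. Week 4 is then also missed, unless the week-4 assessment asks separately, which restores 42 days.

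Weeks 5-7 and 9-11 are uncovered in every one of these variants.

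**Control arm, one-week recall**
- By the described workshop method: 0 of 84 days.
- If the week-12 mark in Table 2 applies to controls: week 12, so 7 of 84 days.
- If the mark in the Session 4 column is also read as a week-4 assessment for controls: weeks 4 and 12, so 14 of 84 days.

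The result is 5-6 weeks against 0-2. Pooled over equal arms, the share of weeks asked about runs from (5 + 0)/24 = 21% to (6 + 2)/24 = 33%.

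**Sensitivity to visit recall, granting controls both visits**

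| Assumed recall at visits | Intervention weeks | Control weeks |
|---|---|---|
| One week at both | 5-6 | 2 |
| Week 12 asks about four weeks | 8-9 | 1 + 4 = 5 |
| Week 12 asks about eight weeks | 11-12 | 1 + 8 = 9 |
| Both ask since the previous assessment | 4 + 8 = 12 | 4 + 8 = 12 |

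Only the last row gives equal coverage, and nothing in the documents states it.

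**Sections side by side.** The Safety section covers every workshop session and does not mention week 12; Table 2 omits Session 1 and includes week 12. Data Management says community partners will not collect data; the Safety section has the facilitators, who are community partners, hand out and review the adverse-event form.

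**The case against.** **Visit recall may be adequate.** The plan mentions a manual of procedures and standardized forms that are not part of this document, and these could set a longer recall and name who asks controls. That is possible, and it is why the size is left open. But an unseen manual cannot be assumed to override the one-week recall that the protocol states.

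**Controls are assessed in the same manner.** Read with Table 2, this could mean that controls are asked at weeks 4 and 12. Granting it gives the 2-week figure above, and still no stated method or assessor.

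**Other routes exist.** This stands, and it limits the point. Serious events go to the investigator as they occur, falls during testing are witnessed, and participants are told what to report and to whom. That last instruction, under Protection Against Study Risks, is tied to taking part in the workshop and so does not clearly reach controls. PROMIS pain scores are scheduled at baseline, week 4 and week 12, but they are an outcome scale and not a record of adverse events.

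**The consequence is modest.** This also stands. The study is described as minimal risk, the pilot saw no injuries, no between-arm test of adverse events is planned, and data go to the DSMB blinded.

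**A stronger reading to avoid.** A reader might infer that weeks 5-7 lie inside the intervention, because the Précis counts the refresher as part of it, and that the plan therefore breaks its own statement about ongoing assessment. The documents do not settle this. The Précis also places week 4 after the intervention, and Design, Interim Analyses and Data Collection all describe a 4-week intervention. The gap does not depend on that reading.

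**Conclusion.** The point holds for elicited non-serious adverse events. The stated rule leaves weeks 5-7 unasked in the intervention arm, no stated recall reaches weeks 9-11, and no method is described for controls. With one-week recall assumed at every contact, coverage is 5-6 of 12 weeks against 0-2.

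The data will therefore be incomplete and probably unequal between arms, but the size is not determined, because it turns on visit recall that the documents do not give. A reader might take the ratio of weeks asked as an estimate of bias in event counts. That is not supported: the ratio of counts would match it only with equal true rates, full attendance and no spontaneous reports, and it falls to 1 if both visits ask since the previous assessment.

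The effect is on the information given to the DSMB and on final safety reporting. The efficacy analysis is untouched. The change is worth making because it is cheap.

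**What to change.** 1. On session and refresher forms, replace the one-week recall with *since the last session you attended*, or *since baseline* at the first session attended.
2. At the existing week-4 and week-12 assessments, give both arms the same short self-completed form with fixed recall: since baseline at week 4, and since the week-4 assessment at week 12. Have it returned sealed, so that blinded assessors do not read it, and opened promptly by existing staff whom the investigator designates.
3. Label each report by source and record the onset date, so that an event on both a session form and a visit form is counted once. Use only the common visit forms for any count by arm.
4. Reconcile the Safety section with Table 2 on Session 1 and week 12, and with Data Management on community partners not collecting data.

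**Cost.** One short form at two existing visits, a wording change, and a source label and onset date in the listing. No new visit is needed.

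**Limits.** Recall over 4-8 weeks is less exact. Intervention participants already prompted at sessions may remember more, so equal weeks asked does not guarantee equal detection. Those who miss an assessment return no form. At the plan's anticipated attrition of about 20% (8 of 40 per arm), the two forms would cover 32 × 12 = 384 of 480 person-weeks (80%) if all losses came before week 4. If all came after week 4, they would cover 40 × 4 + 32 × 8 = 416 of 480 (87%).
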